The current study describes the formative testing of a web-based indoor tanning intervention that adapts the general PFI approach of assessment and tailored feedback related to users' tanning beliefs and behavior. This novel tanning intervention approach is designed to better address the unique psychological motivations for tanning among frequent indoor tanners and utilizes a behavior change framework that has been shown to be successful in changing addictive behaviors. Our study also introduces some innovations to the typical PFI approach. Rather than deliver feedback after the initial assessment, our intervention provides feedback in real-time as users progress through the assessment. This approach is intended to produce more meaningful reflection of intervention content. We also supplemented the web intervention, designed primarily to motivate openness to change, with a series of four weekly booster interventions designed to encourage change planning, behavior monitoring, and building self-efficacy, all critical skills in successful behavior change. These modifications were designed to offer an experience that more closely aligns with a traditional, in-person delivery approach.

In this study, we report results from a randomized control trial of the intervention among a sample of young adult women engaged in frequent indoor tanning. Our study was designed to examine intervention acceptability and engagement. We also assess the preliminary impact of the intervention by comparing the tanning bed behaviors of intervention recipients compared to a waitlist control condition. Finally, we explore putative mediators of the intervention by evaluating intermediate intervention outcomes consistent with PFI behavior change principles including readiness to change and self-efficacy.

METHODS

Participants and Recruitment

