Study eligibility criteria included women between 18 - 25 years of age engaged in frequent tanning bed use, which was defined as at least 25 indoor tanning sessions in the past 12 months. Participants were recruited using multiple approaches. Qualtrics Sample Providers emailed study advertisements with links to a brief online eligibility screening survey to members of internet panels and posted online advertisements. The screening survey was programmed to present eligible participants with a brief description of the intervention trial and a question to indicate their interest in receiving an email study invitation. Second, recruitment flyers with study personnel contact information were posted on campus and in classrooms at a large Northeastern University and on internet ads on social media and Craigslist. Most participants (96%) were recruited by Qualtrics.

Study Design and Procedure

The study was a 2-arm randomized controlled trial with planned 1:1 allocation. A study coordinator enrolled participants, administered all procedures, and monitored trial progress. Following screening, the study coordinator sent an invitation email with a link to the online baseline survey, programmed using Qualtrics survey software, and a unique study personal identification number (PIN) for accessing the survey. Each PIN was assigned to a study condition, and we used a random number generator to randomly order the PINs in our study tracking spreadsheet. PINs were assigned to participants in order of our receipt of their screening survey and prior to sending the baseline survey invitation. Participants were asked to provide online informed consent prior to beginning the baseline survey and those who did not were not provided access to the survey. Up to three email reminders were sent to individuals who agreed to participate. Links to the web-based intervention were sent to participants two weeks after completing the baseline survey. A brief intervention evaluation survey was presented immediately after participants completed viewing the intervention. All participants who completed the baseline were invited to complete the follow-up assessment 12 weeks later. Participants assigned to the waitlist control were invited to access the intervention after the follow-up surveys concluded. Participants received a gift card for completing the baseline survey, the intervention

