Primary Outcomes. The primary outcomes of indoor tanning bed use, sunburns, and indoor tanning intentions were assessed at both the baseline and follow-up surveys. Participants were asked to recall the number of indoor tanning sessions they had in the past two months. A similar question format was used to assess the number of sunburns they received in the past two months. Sunburns are a commonly-experienced side-effect of tanning bed use and independent risk factor for skin cancer risk (Stapleton et al., 2013). Our measure did not specify if reported sunburns were a result of indoor tanning so the measure is considered to be a general marker of ultraviolet risk behavior. For tanning intentions, participants indicated how likely they were to use an indoor tanning bed in the next year on a 6-point response scale anchored with 1 = *Extremely unlikely* and 6 = *Extremely likely* (Hillhouse et al., 2008).

Exploratory Outcomes. Interest in changing tanning was assessed using a single item (Would you like to reduce or quit indoor tanning if you could do so easily?) adapted from Sobell and colleagues' (1996) questions about readiness to change drinking behaviors (responses coded as 0 = *no* and 1 = *yes*). Self-efficacy in quitting tanning was assessed using Zeller and colleagues (2006) single item assessing perceived difficulty in quitting tanning (How hard would it be for you to stop using tanning beds/booths? (*Please answer on a scale for 0-10, where 0 is "Not at all hard", 10 is "Extremely hard"*)).

Statistical Analyses Plan

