Acceptability and engagement metrics are described for all participants who completed the intervention evaluation. We compared intervention and control participants on their baseline responses for the primary study outcomes and found evidence of non-equivalence. Specifically, intervention participants reported disproportionately higher rates of lifetime indoor tanning use ($M_{\text{intervention}} = 409.0$, $M_{\text{control}} = 158.5$) and 12-month indoor tanning ($M_{\text{intervention}} = 72.3$, $M_{\text{control}} = 49.0$) compared to control participants. A series of 2 (condition) X 2 (time) mixed-measures analysis of variance (ANOVA) was used to examine differences in study outcomes to control for baseline differences between conditions. Our power calculations indicated that a sample size of 54 participants would allow us to detect a moderately large intervention effect (specifically, 80% power to detect an 8 IT session difference between conditions).

Table 1. Intervention map with the goals and brief descriptions of intervention content.

Goal	Content and Description
Enhance interest and readiness to change	Self-exploration of tanning ambivalence. Participants were encouraged to answer open and close-ended questions in which they described individual patterns of indoor tanning bed use and experiences with tanning. Additional personalized feedback tailored to participant responses encouraged reflection on the balances of pros and cons of indoor tanning.
Bolster commitment to change	Normative beliefs about IT. Participants were asked to estimate the percent of women their age who use IT. Following this exercise, participants were provided with the actual percent of women compared to what they believed to be true.
	Desired motives and values. Tanners were asked questions designed to clarify their most important desired motives or values. Through a series of close-ended questions, participants were then encouraged to think about the good and not-so-good aspects of indoor tanning. Following this exercise, personalized feedback was provided to the participant aligning their personal values with the pros and cons of indoor tanning.

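### The two-time mixed ANOVA compares raw change without conditioning on baseline, so dropout that depends on baseline tanning differently by arm can bias it, and it does not deliver the stated control for baseline differences

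*Combined protocol and SAP*

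**What the plan says.** The combined document, under Statistical Analyses Plan, reports that the arms were not equivalent at baseline: mean 12-month indoor tanning was 72.3 in the intervention arm and 49.0 in control. It then gives the only analysis of outcomes: "A series of 2 (condition) X 2 (time) mixed-measures analysis of variance (ANOVA) was used to examine differences in study outcomes". The stated purpose is "to control for baseline differences between conditions". Under Measures, the primary outcomes ("indoor tanning bed use, sunburns, and indoor tanning intentions were assessed at both the baseline and follow-up surveys") have two time points and no others.

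Under Study Design and Procedure, "All participants who completed the baseline were invited to complete the follow-up assessment 12 weeks later". The trial planned 1:1 allocation, and the study number that carried the condition was issued early: "PINs were assigned to participants in order of our receipt of their screening survey and prior to sending the baseline survey invitation".

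An analysis set is stated only for acceptability and engagement. For the outcome analysis the document gives no analysis set, no rule for missing follow-up, and no expected or observed dropout. The sample size statement gives 54 participants and 80% power for a difference of 8 sessions, without an SD, a correlation or a dropout allowance.

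**The concern.** A classical 2 x 2 mixed ANOVA uses only people with both measurements. A woman without the 12-week survey drops out of the analysis together with her baseline. The condition-by-time F is then the square of a two-sample t statistic on follow-up minus baseline. Baseline enters as the first repeated measure and is not conditioned on.

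This matters for two reasons. First, women with high baseline counts tend to fall back towards the mean and women with low counts tend to rise. If dropout leaves the arms with different baseline means, the difference in mean change moves even when the intervention does nothing. ANCOVA on the same completers does not have this problem when dropout depends only on baseline. Second, the same feature acts on any imbalance already present at baseline, and controlling for that imbalance is the reason the plan gives for choosing the model.

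Dropout that differs by arm is plausible, though not shown. The intervention arm has a web session designed for 30 minutes or less and four 5-minute weekly boosters, while control women have no study content before follow-up.

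**Working it through.** **1. The plan's own figure.** N = 54 cannot be reproduced, because no SD or alpha is given. It can be solved backwards. With 27 per arm, a difference of 8, two-sided 5% and 80% power:

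SD = 8 / [(1.96 + 0.842) x sqrt(2/27)] = 10.5, or 10.3 by the noncentral t. I use 10.3 as an assumed SD for session counts at each time.

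**2. Formula.** Let b be the slope of follow-up on baseline. With equal SDs at the two times, b equals the correlation. If there is no true effect and dropout depends only on baseline, then

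bias of the change contrast (intervention minus control) = (b - 1) x D,

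where D is the completers' mean baseline in the intervention arm minus that in control. ANCOVA estimates the arm difference at a given baseline value, so D drops out of it.

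**3. Illustration.** All inputs are assumed: normal outcomes, SD 10.3, dropout of 30% in the intervention arm and 15% in control, and a logistic dropout model with log-odds rising 0.7 per SD of baseline. The completers' baseline means come from integrating that model.

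| Dependence on baseline | Completers' baseline shift, intervention / control | D | Bias at b = 0.3 | b = 0.5 | b = 0.7 |
|---|---|---|---|---|---|
| Intervention arm only | -1.97 / 0 | -1.97 | +1.4 | +1.0 | +0.6 |
| Both arms | -1.97 / -1.02 | -0.96 | +0.7 | +0.5 | +0.3 |
| Neither arm | 0 / 0 | 0 | 0 | 0 | 0 |

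For example, row 1 at b = 0.5 is (0.5 - 1) x (-1.97) = +0.99. Large-sample simulation of row 1 gave 1.37, 0.98 and 0.59, with ANCOVA on the same completers within 0.02 of zero. A reduction in tanning is negative, so a positive bias hides benefit. As shares of the 8-session target, row 1 is 0.6/8 = 7% to 1.4/8 = 17%, and row 2 is 0.3/8 = 4% to 0.7/8 = 8%.

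**4. When there is no bias.** Bias is zero if dropout is unrelated to baseline, even at different rates (row 3). It is also zero if dropout is the same function of baseline in both arms with balanced baselines, or if b = 1.

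**5. No dropout at all.** The 12-month imbalance is 72.3 - 49.0 = 23.3 sessions. The two-month baseline means are not given. Spread evenly over the year (an assumption), the imbalance is 23.3/6 = 3.9 sessions per two months. Treating it as a chance difference, the change contrast is off by (b - 1) x 3.9:

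- b = 0.3: -2.7
- b = 0.5: -2.0
- b = 0.7: -1.2

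The sign is negative, which flatters the intervention. With SD 10.5 and the same dropout function in both arms (log-odds 1 per SD, about 18% to 23% lost), the values are -2.4, -1.7 and -1.1. That error is regression to the mean and is not caused by dropout.

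**The case against.** The strongest reply is that nothing here shows a biased result. The documents report no dropout, and restriction to completers is inferred from the method, since the text does not say it. Three conditions must hold together: dropout related to baseline, a rate or dependence that differs by arm, and a slope other than 1. All of this stands.

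The dropout bias is also small beside the sampling error. With 54 enrolled and SD 10.3, the standard errors in the intervention-arm-only case are about 3.8, 3.2 and 2.5 sessions at correlation 0.3, 0.5 and 0.7. The bias is then 0.24 to 0.37 of a standard error, and type I error rises to only about 5.7% to 6.6%. For a formative trial of preliminary impact that is modest. A gift card for the follow-up survey, given in both arms, may also limit dropout. This bears on the weight of the point, but not on whether a better method is available at no cost.

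A reader might infer three stronger things that the documents do not support:

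- **Unequal dropout alone biases the test.** It does not; see step 4.
- **Women who never opened the intervention were excluded.** The aims paragraph speaks of "comparing the tanning bed behaviors of intervention recipients compared to a waitlist control condition", but that sentence describes aims and does not define an analysis set. The analysis plan compares by condition, and every baseline completer was invited to follow-up. No size can be attached to this reading.
- **Control women stayed because a later intervention had been promised.** The document says they were invited to it after the follow-up surveys ended. It does not say when they were told.

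**Conclusion.** The point holds as a conditional weakness of the chosen model. The mixed ANOVA compares raw change and does not condition on baseline, so it is open to bias from baseline-related dropout that differs by arm. Under the assumed 30% versus 15% dropout the size is 0.3 to 1.4 sessions, in the direction of hiding benefit when heavier tanners leave the intervention arm. The actual size and direction are unknown.

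The same feature defeats the model's stated purpose even with complete follow-up. On the assumed 3.9-session imbalance the contrast is off by 1.2 to 2.7 sessions, which is larger than the dropout figures and opposite in sign.

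All figures rest on an assumed SD, normal outcomes and correlations of 0.3 to 0.7; session counts are likely to be skewed. They are for tanning sessions only; the other primary outcomes share the mechanism but were not sized. This is an improvement worth making, and it is not evidence that the trial's result is wrong.

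**What to change.** Replace the mixed ANOVA with ANCOVA: for each primary outcome, regress the follow-up value on condition and the baseline value of that outcome. Baseline 12-month sessions may be added as a covariate. State that women are analysed in the arm assigned, whether or not they opened the intervention. Report retention by arm and by baseline tanning, so that a reader can judge whether the conditions for bias were met.

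A likelihood-based repeated-measures model that keeps women with a baseline only is an acceptable alternative. If it constrains the arms to a common baseline mean, that needs justification, because condition was assigned before consent and the baseline survey, and the arms were found to differ.

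The cost is slightly different analysis code and a few sentences in the plan. The baseline values are already collected, so no new data are needed.

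### The 2 × 2 mixed ANOVA controls for baseline differences only in part: its interaction is a change-score test, and the two variables reported as imbalanced are not in the model

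*Combined protocol and SAP*

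**What the plan says.** The Statistical Analyses Plan first describes a baseline check: "We compared intervention and control participants on their baseline responses for the primary study outcomes and found evidence of non-equivalence". As evidence it states that "intervention participants reported disproportionately higher rates of lifetime indoor tanning use" (means 409.0 v 158.5) and gives a similar gap for "12-month indoor tanning" (72.3 v 49.0). It then says that a series of 2 (condition) × 2 (time) "mixed-measures analysis of variance (ANOVA) was used to examine differences in study outcomes to control for baseline differences between conditions". Condition and time are the only terms named. No covariate is listed, and the plan does not say whether the interaction or the condition main effect is the intervention test.

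Measures, Primary Outcomes, defines what enters these models: "The primary outcomes of indoor tanning bed use, sunburns, and indoor tanning intentions were assessed at both the baseline and follow-up surveys". For tanning, "Participants were asked to recall the number of indoor tanning sessions they had in the past two months", and sunburns use the same window.

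Under Study Design and Procedure, each PIN already carried a study condition, and "PINs were assigned to participants in order of our receipt of their screening survey and prior to sending the baseline survey invitation".

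**The concern.** The plan sees an imbalance, names a model, and says that the model deals with it. Three things do not fit.

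- The variables shown to be imbalanced are lifetime and 12-month use. The text offers them as baseline values of the primary outcomes, but those are two-month sessions, two-month sunburns and intentions.
- Neither variable is a term in the model. Twelve-month use is represented only so far as it overlaps the two-month baseline window. Lifetime use is represented still less.
- With two waves, the interaction subtracts the baseline value in full and does not estimate how well baseline predicts follow-up. That usually wastes precision in a trial planned around 54 participants.

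At stake are precision for all three primary outcomes and, for sessions only, an estimate whose meaning depends on why the arms differed at baseline. If the condition main effect were read as the intervention effect, baseline would be averaged into the effect and not adjusted for.

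**Working it through.** **1. The plan's own figure.** The plan states 54 participants and "80% power to detect an 8 IT session difference between conditions". It gives no SD, alpha or correlation, so 54 cannot be reproduced; only the implied SD can be solved. Reading 54 as the total (27 per arm) and assuming two-sided 0.05: 8 / [(1.960 + 0.842) × √(2/27)] = 8 / 0.762 = 10.49 sessions, or 10.30 from the t-test version. This SD is inferred, not documented.

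**2. What the interaction tests.** With two waves, the condition × time F equals the square of the two-sample t on follow-up minus baseline. A numerical check gave 0.12953 for both.

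**3. Precision.** Let ρ be the baseline to follow-up correlation and k the baseline SD divided by the follow-up SD. In units of follow-up variance, per arm:

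- change score: k² + 1 − 2ρk
- ANCOVA on baseline: 1 − ρ²
- ratio: (k² + 1 − 2ρk)/(1 − ρ²) = 1 + (k − ρ)²/(1 − ρ²), which is never below 1

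| | ρ = 0.3 | ρ = 0.5 | ρ = 0.7 |
|---|---|---|---|
| k = 0.7 | 1.07/0.91 = 1.18 | 0.79/0.75 = 1.05 | 0.51/0.51 = 1.00 |
| k = 1, ratio 2/(1 + ρ) | 1.54 | 1.33 | 1.18 |
| k = 1.4 | 2.12/0.91 = 2.33 | 1.56/0.75 = 2.08 | 1.00/0.51 = 1.96 |

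Simulation at k = 1 with 27 per arm (20,000 runs) gave 1.51, 1.31 and 1.15. The small shortfall is the cost of estimating the slope.

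**4. Direction of bias, sessions only.** Assume steady use, so that the 12-month gap is (72.3 − 49.0)/6 = 3.88 sessions per two months, and equal correlation ρ between two-month windows.

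- *Chance gap.* Given the 12-month gap, the expected baseline gap is 3.88 and the expected follow-up gap without any effect is 3.88 × 6ρ/(1 + 5ρ). The interaction therefore shifts toward the intervention by 3.88 × (1 − ρ)/(1 + 5ρ) = 1.09, 0.55, 0.26 sessions at ρ = 0.3, 0.5, 0.7. ANCOVA on baseline and 12-month use has no expected shift.
- *Stable gap.* The interaction has no expected shift. The same ANCOVA errs by the same 1.09, 0.55, 0.26 against the intervention.
- *Stable gap, correlation decaying with time (AR(1)).* ANCOVA errs by 3.88 × (1 − ρ) = 2.72, 1.94, 1.17 against the intervention. Simulation gave 2.71, 1.96 and 1.20, with two-sided type I error of 15%, 11.5% and 8.7%.

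These session figures come from a normal-data model with raw 12-month use and SD 10.3. They illustrate direction and do not describe an analysis using log 12-month use.

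**5. Main effect.** The condition main effect is the mean of the baseline and follow-up gaps. With a stable gap of 3.88 and a true reduction of 8, it is (3.88 + (3.88 − 8))/2 = −0.12, so a real effect would almost vanish.

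**The case against.** The strongest defence is that the planned test is valid. Over repeated randomisation a change-score comparison is unbiased, and it does remove each outcome's own baseline gap. Twelve-month use would ordinarily include the two-month baseline window, so it is not wholly absent. The trial is described as formative and its impact analysis as preliminary. All of this stands, and it is why the finding is partial control and not failed control.

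The precision argument also has limits. The gain is an average over randomisations. In simulated trials with a baseline gap above 0.3 SD on the outcome itself, the variance ratio fell to 1.03, 1.00 and 0.97 at ρ = 0.3, 0.5 and 0.7. For sunburns and intentions, however, no such gap is reported.

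A reader might infer that the interaction is biased in favour of the intervention. The documents do not support that. It holds only if the gap is chance. PINs tied to condition were assigned before consent and baseline, so a stable difference between those who enrolled cannot be ruled out; nor do the documents show that one arose. A reader might also infer that ANCOVA should simply replace the interaction for sessions. Under a stable gap with decaying correlation that would raise type I error to between about 9% and 15%, while the interaction stays near 5%. The choice is a trade-off.

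Finally, the absence of baseline two-month sessions, sunburns and intentions by arm from this text does not show that they were never tabulated. Measures cites a Table 3 that this file does not contain.

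**Conclusion.** The statement that the ANOVA controls for baseline differences is only partly true and should be changed. Two parts are certain from the text and algebra: the two-wave interaction is a change-score test, and lifetime and 12-month use are neither defined primary outcomes nor model terms. Confidence here is high.

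Confidence in the size is medium, because ρ and every SD are assumed. With equal SDs the variance penalty against baseline ANCOVA is 18% to 54% for ρ from 0.7 to 0.3. Allowing baseline SD to be 0.7 to 1.4 times follow-up SD, it runs from nil to 133%.

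For sunburns and intentions only precision is at issue, and ANCOVA is a clear improvement using data already collected. For sessions the documents cannot tell a chance gap from a stable one, so neither model can be called the less biased. No power figure is offered for the log-adjusted session model, because none has been worked out for it.

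**What to change.** 1. **Sunburns and intentions.** Make the primary analysis ANCOVA, or its generalised-linear equivalent, of follow-up on condition and the outcome's own baseline. Report the adjusted difference with its 95% CI.
2. **Two-month sessions.** Report side by side the condition × time interaction and an ANCOVA adjusting for baseline sessions and log 12-month use. Add log lifetime use as a sensitivity analysis only: taking ln(409.0/158.5) = 0.948 as the gap and assuming a log SD of 0.8, 1.0 or 1.2, variance inflation 1 + d²/4 is 1.35, 1.22 or 1.16, which widens the CI by about 16%, 11% or 8%. Label the 12-month and lifetime adjustments post hoc, report every analysis whatever it shows, and state that disagreement means the result depends on whether the baseline gap is chance or stable.
3. **Test term.** Name the condition × time interaction as the ANOVA effect of interest, and do not interpret the condition main effect as the intervention effect.
4. **Wording and reporting.** Replace the unqualified claim of control with one saying that the interaction subtracts each outcome's own baseline gap. Correct the sentence that presents lifetime and 12-month use as primary-outcome baselines. Report baseline two-month sessions, sunburns and intentions by arm.

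The cost is wording, a re-run on existing data, and one degree of freedom for sunburns and intentions, two for sessions, or three with lifetime use. Adjustment cannot be guaranteed to remove any selection that arose after PINs were assigned.

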Our theoretical intervention is grounded in Motivational Interviewing (MI) principles designed to motivate individuals to make changes in addictive behaviors (Miller and Rollnick, 2012). A fundamental MI principle is that individuals who engage in risky behavior like tanning experience a natural state of behavioral ambivalence, which is defined as holding both positive and negative views of the behavior. Traditionally, MI has been used to inform the way that trained counselors deliver in-person therapy

sessions related to reducing risk behaviors among clients. Such sessions are designed to promote self-exploration of ambivalence by encouraging individuals to reflect on both the positive and problematic aspects of behaviors. This exploration is intended to make the negative aspects of behavior more salient and produce an increased openness to changing behavior, the first step in the behavior change process. Among individual who are open to changing, the MI approach increases the commitment to make a change and provides behavior change strategies to boost self-efficacy and likelihood of making a successful change (Miller and Rollnick, 2012). Although MI-based interventions have not been thoroughly tested in the context of changing tanning behavior, studies show tanners perceive aspects of their tanning to be problematic, perceive advantages to reducing their tanning, and are receptive or actively trying to change their tanning (Banerjee et al., 2014; Glanz et al., 2018; Harrington et al., 2011; Mosher and Danoff-Burg, 2010). This evidence that some tanners experience behavioral ambivalence and report an openness to changing their tanning behavior suggests adopting an MI approach to tanning interventions may be appropriate.

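### The exploratory yes/no readiness item falls under a change-score ANOVA; a binary comparison conditioned on the baseline answer suits it better (minor)

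*Combined protocol and SAP*

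**What the plan says.** Under Measures, Exploratory Outcomes, readiness is a single question: "Interest in changing tanning was assessed using a single item (Would you like to reduce or quit indoor tanning if you could do so easily". Answers are coded 0 for no and 1 for yes.

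The introductory text, just before Methods, gives the item its role: "we explore putative mediators of the intervention by evaluating intermediate intervention outcomes", with readiness to change and self-efficacy as the examples. Table 1 lists enhancing interest and readiness to change as the intervention's first goal.

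The Statistical Analyses Plan names one comparative method, a series of 2 (condition) by 2 (time) mixed ANOVAs. It reports that the arms differed at baseline in lifetime and 12-month tanning, and says that the ANOVA "was used to examine differences in study outcomes to control for baseline differences between conditions". It names no logistic, exact or other categorical method. The only power statement is for tanning sessions: "a sample size of 54 participants would allow us to detect a moderately large intervention effect", specified as "80% power to detect an 8 IT session difference between conditions".

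Two readings are inferred. The plan does not say outcome by outcome that the ANOVA applies, but it offers nothing else for this item. Measurement at both baseline and follow-up is stated only for the primary outcomes and is assumed here for readiness too.

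**The concern.** A change in a 0/1 answer can only be -1, 0 or +1. A woman who says *yes* at baseline can only stay or fall, and one who says *no* can only stay or rise. Mean change in an arm therefore depends on how many women happened to say *yes* at the start. A test on change does not remove that dependence; conditioning on the baseline answer does.

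At stake are the precision and readability of one of the two putative mediators. A real shift in readiness could be missed more often than the data require. The result would also appear as a mean change on a 0/1 scale rather than as percentages of women.

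**Working it through.** **1. The plan's own figure.** Sessions: 54 participants, 80% power, 8-session difference. No SD or alpha is given. Taking 27 per arm (1:1 allocation) and two-sided 5%, n per arm = 2(1.960 + 0.842)² SD²/8². Setting n = 27 gives SD² = 27 × 64/(2 × 7.85) = 110, so SD is about 10.5 and d about 0.76. Without a stated SD the figure can be neither confirmed nor refuted. It says nothing about the readiness item.

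**2. What the ANOVA tests.** With two time points, the condition-by-time F test equals the squared t test comparing mean change between arms.

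**3. Baseline imbalance.** In one arm let p be the baseline *yes* share, s the probability of staying *yes* and c the probability of moving to *yes*. Then

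mean change = (1 - p)c - p(1 - s) = c - p[1 - (s - c)].

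Each extra 10 points of baseline *yes* in the intervention arm lowers the estimated effect by 10 × [1 - (s - c)] points:

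- s = 0.9, c = 0.1: 2 points
- s = 0.8, c = 0.2: 4 points
- s = 0.6, c = 0.4: 8 points
- s = 1, c = 0: none

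In the random-intercept simulations below, with SD 1 to 4, the slope was -0.40 to -0.92, or 4 to 9 points per 10. Such imbalances are ordinary at this size: the SD of the chance difference in baseline share is √(2p(1 - p)/27), which is 0.14 at p = 0.5 and 0.10 at p = 0.85.

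**4. Power, random-intercept logistic model.** Assumptions: 27 per arm, no dropout, conditional odds ratio 5, two-sided 5%, 6,000 trials per setting. Baseline *yes* is 50/70/85%. The random-intercept SD sets the baseline/follow-up correlation (phi).

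| SD | phi | ANOVA interaction, % | Stratified CMH, % | Gap, points |
|---|---|---|---|---|
| 1.5 | 0.22-0.29 | 36/25/14 | 53/41/24 | 17/16/10 |
| 3 | about 0.5 | 26/19/12 | 33/27/16 | 7/8/4 |
| 4 | 0.58-0.63 | 21/17/11 | 26/22/13 | 5/5/2 |
| 5 | about 0.7 | 18/15/10 | 22/18/11 | 4/3/1 |

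Repeat runs at SD 1.5 gave gaps of up to 18 points. The simulation standard error is about √(0.2 × 0.8/6000) = 0.5 points at 20% power, so a 1-point gap is close to noise. The conditional odds ratio is fixed, so the effect in percentage points shrinks as SD rises. Compare within rows, not down columns.

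**5. Power, transition model.** Here the intervention adds 40 points to the probability of moving to *yes*; 27 per arm, 40,000 runs per scenario. Two unadjusted tests of the follow-up answer are added.

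| Baseline *yes* | Control s, c | Control phi | ANOVA | Follow-up chi-square | Fisher | Stratified CMH |
|---|---|---|---|---|---|---|
| 0.5 | 1.0, 0 | 1.00 | 0.82 | 0.31 | 0.23 | 0.83 |
| 0.5 | 0.9, 0.1 | 0.80 | 0.40 | 0.32 | 0.23 | 0.48 |
| 0.7 | 0.9, 0.1 | 0.77 | 0.18 | 0.18 | 0.10 | 0.23 |
| 0.5 | 0.8, 0.2 | 0.60 | 0.28 | 0.32 | 0.23 | 0.38 |
| 0.5 | 0.6, 0.4 | 0.20 | 0.19 | 0.31 | 0.23 | 0.31 |

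Over all scenarios (baseline *yes* 0.3 to 0.8) CMH exceeded the ANOVA by 0 to 13 points at phi of 0.5 or more, and by about 1 to 28 points below that.

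**6. Type I error.** Null rejection was 2.4 to 5.3% for the ANOVA in the transition model and 4.2 to 5.4% in the random-intercept model. For CMH it was 2.1 to 5.1% and 4.4 to 5.4%. The low values arise when almost nobody changes her answer.

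**7. Exact version.** At SD 1.5 a conventional exact stratified test had power 42/29/11%, against 36/25/14% for the ANOVA. At SD 3 and 5 it fell to about the ANOVA's level or below. Cells are sparse where it would be invoked: at 85% baseline *yes*, about 0.15 × 27 = 4 women per arm can move up.

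**The case against.** The strongest case for leaving the plan alone is that the item is exploratory, the study is formative, no power is claimed for readiness and the ANOVA keeps its error rate. All of that stands, and it is why the point is minor. Under randomisation the change-score estimate is also unbiased on average; the dependence in step 3 is on the imbalance that happens to occur.

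A reader might infer several stronger points that the documents do not support:

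- **That the ANOVA is well below any simple binary test.** It is not. Against an unadjusted follow-up chi-square, the ANOVA is usually equal or better at high phi (0.82 against 0.31 at phi 1.0). It beats Fisher's test in every transition scenario with phi of 0.5 or more. The advantage belongs to conditioning on baseline.
- **That the ceiling is a fault of the ANOVA.** It belongs to the item. Women already at *yes* cannot move up under any method, and CMH power at 85% baseline *yes* is itself only 24% at SD 1.5.
- **That the baseline *yes* rate must be high.** The introduction cites other samples in which tanners "are receptive or actively trying to change their tanning", then concludes only that some tanners are open to change. No rate is given for this sample.
- **That the arms were imbalanced on readiness.** The reported differences concern lifetime and 12-month tanning, not this item.

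**Conclusion.** The concern holds as a minor point. As written, the plan applies a change-score test to a yes/no item. Its estimate moves against chance baseline imbalance by about 4 to 9 points per 10-point imbalance under the random-intercept assumptions, and by less if answers rarely change. Its power is at or below that of a baseline-stratified binary test: by about 10 to 18 points at phi 0.2 to 0.3, 4 to 8 at about 0.5, and 1 to 5 at about 0.6 to 0.7. The transition model widens the range at phi of 0.5 or more to 0 to 13.

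These sizes rest on assumed baseline rates, repeatability and effects, 27 per arm, no dropout, and measurement at both times. Power is low for every method in most settings, so the change helps without making the item well powered. No primary conclusion depends on it.

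**What to change.** For this item only, replace the mixed ANOVA in the Statistical Analyses Plan with a comparison of the follow-up yes/no answer conditioned on the baseline answer. Use the asymptotic CMH test stratified by baseline answer or, in effect equivalently, the score test from a logistic model with baseline answer as covariate. Report the baseline-adjusted risk difference with a 95% CI. Tabulate by arm how many baseline-*no* women moved to *yes* and how many baseline-*yes* women stayed there, which also shows the baseline rate in each arm. State that the item is measured at both surveys.

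Do not make the conventional exact test the default, because it is conservative and loses most or all of the gain. If cells are sparse, use a mid-p version and accept somewhat lower power.

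The cost is a few lines of text and a standard procedure, with no new data if the item was asked at both surveys. The small downside is that readiness is then reported on a different scale from the other outcomes.
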